Dysphagia is the term for symptomatic swallowing difficulties in patients. Swallowing is known to be a complex neuromuscular function with innervation from the pharyngeal plexus, the ansacervicalis, and cranial nerves IX, X, and XII. Virtually all patients will have some swallowing difficulty immediately after an anterior cervical spine procedure (1). The primary cause of this dysphagia is not believed to be denervation from the surgical approach but rather edema and late fibrosis in the esophageal tissue from the pressure of retractors (2,3). This has been shown histologically in a sheep study done by Cavusoglu et al (4). Other factors contributing to postoperative dysphagia include the presence of an anterior plate, the number of operative levels, higher levels of the cervical spine (such as C3-C4), duration of surgery, hematoma, and female gender (5-8).

Despite the anterior approach for cervical surgery having been popular for decades, it is only in the last several years that better studies have clarified the problem. In 2002, Bazaz et al. documented higher percentages of dysphagia months after surgery than had previously been known (9). These investigators obtained patient-reported symptoms at various time points up to one year following anterior cervical surgery. They developed a scale of none, mild, moderate, and severe symptoms of dysphagia and reported on 249 patients. The incidence of symptomatic swallowing difficulty was a surprising 50% at one month, 32% at two months, 18% at six months, and 12.5% at 12 months. Moderate to severe symptoms were still noted in 4.8% of patients six months post-operatively. Similarly, Riley et al. published on a large Cervical Spine Research Society cohort of 534 patients. Their data also showed a substantial percentage of symptoms three months post-operatively (29%). Six percent of patients still had some dysphagia 24 months post-operatively (10).

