This investigation is a prospective, randomized, double-blind, controlled trial testing peri-operative steroids versus saline and the effect on swallowing after anterior cervical spine surgery. Persons between the ages of 18 and 80 undergoing anterior cervical decompression and stabilization procedures for degenerative conditions are eligible for the study. This would include persons undergoing anterior cervical discectomy and fusion (ACDF), hybrid constructs, corpectomy(ies), and disc arthroplasty. Persons excluded from the study include those with major trauma, neoplastic, or infectious conditions requiring surgery. Also excluded are persons undergoing anterior-posterior operations, those with a history of previous anterior cervical spine surgery, any one requiring a halo vest, persons on chronic steroids, and persons remaining intubated postoperatively.

Swallowing symptoms will be measured using the patient reported Bazaz scale and the Dysphagia Short Questionnaire. Swallowing data will be obtained pre-operatively, one day and two days post-operatively and then one week, two weeks, four weeks, three months, six months, and one year post-operatively. Other data to be collected for analysis includes patient comorbidities, levels and type of surgery, intra-operative fluids, estimated blood loss, type of retractors, type of brace if any, length of stay, and other surgically related complications. Patient clinical outcomes will be captured using our web-based progress reports.

Participants in this study will complete the QoL-12, Neck Disability Index, and Visual Analog Scale questionnaires electronically pre-operatively and at one month, three months, six months, and one-year post-operative time points. This outcome data will help us analyze the swallowing function or symptoms with the overall clinical course of the participants enrolled in this study.

Inclusion Criteria:

- Elective anterior approach to subaxial cervical spine (C3 - T1)
- Ages 18-80

Exclusion Criteria

- Traumatic or tumor etiologies
- undergoing anterior-posterior operations
- neoplastic, or infectious conditions requiring surgery
- a history of previous anterior cervical spine surgery
- any patient requiring a halo vest
- patients on chronic steroids
- patients remaining intubated post-operatively (please see more under risks below)
- less than 18 years of age
- pregnant women
- no phone

Procedures

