Persons who have chosen to undergo anterior cervical spine surgery will be seen at the clinic for a pre-operative visit. The surgeons on the protocol will discuss the study and the subjects will be given the opportunity to participate. If the subjects agree to participate, a consent form will be administered by a member of the research team. The Bazaz and Dysphagia Short Questionnaire will be administered to subjects at this visit prior to surgery and again at Day 1, Day 2, 1 week, 2 weeks, 1 month, 3 months, 6 months, and 12 months after surgery. If the subject does not come for a clinic visit at the follow up times, he/she will be called to answer the questions on the surveys. The windows-of-time in which subjects may be called after discharge include: for follow up for week 1 and week 2, two days before or after the actual day of 1 or 2 weeks; for week 4, three days before or after the actual day of 4 weeks; for 3 months and 6 months, a week before or after the actual date of 3 or 6 months; for 1 year, 2 weeks before or after the actual date of 1 year. Subjects will be randomized to either the steroid administration group or the saline administration group. Subjects randomized to the experimental (steroid) group will receive 0.3 mg/kg of intravenous dexamethasone within one hour of the incision, then 0.15 mg/kg every eight hours (window of time 45 minutes on both ends of the eight hour time, e.g. if the time is 8 pm, the dose could be given from 7:15 pm through 8:45 pm) for two doses. This dosage is approximately 20 mg, 10 mg, and 10 mg of dexamethasone. Subjects in the control (saline) group will receive a similar volume of saline on the same schedule for three doses. This is a double-blind trial; the surgeon (and anesthesiologist) and the subject will not know what group assignment the subject has received. The in-patient pharmacy will generate IV bags that are labeled for the study but that are blinded as to medication/saline labels. Randomization will be performed by the satellite pharmacist outside of the operating room. This person will also supply the study drug.

Sample Size

70

Sample Size justification

Our power analysis indicates 64 subjects with 32 in each arm is enough to give us 81% power to reject the null hypothesis. We are adding an additional 10% to that number as we expect to have a loss to follow up of approximately 10%.

Data Analysis

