Power and sample size calculations are based on the presence or absence of dysphasia at 2-weeks. Based on a literature review we postulated that 50% of the subjects in the control arm would experience mild, moderate or severe dysphasia. If that figure can be improved to the point where just 20% of the subjects are similarly affected, then that, in our opinion, would represent clinical success. Under the above scenario, 32 subjects in each arm would give us 81% power to reject the null hypothesis. We plan to analyze the data in two ways. First, we will look at the time-to-event where the event is "no dysphasia" in a discrete time survival model. Second, we will use a repeated measures ordinal categorical model to assess the effect of steroid/control in a generalized linear model. We have an electronic database that we will use to track patient outcomes. If subjects are unable to return to clinic, they will be able to complete the database questionnaires online. Our clinical research coordinator will also be able to contact subjects via phone to complete the Bazaz scale and Dysphagia Short Questionnaire.

Potential Risks/Discomforts/Privacy

Completion of the Bazaz scale and Dysphagia Short Questionnaire may cause some discomfort. The only expected side effect, in the group receiving steroids, would be possible elevation of serum glucose levels in diabetic subjects. The serum glucose levels in diabetic subjects will be monitored postoperatively with routine postoperative laboratory testing. All other procedures are standard of care.

Potential subjects will be recruited/consented for the study in private rooms at the Physician Office Center (POC) when they come for their History and Physical visit prior to surgery. All HIPAA safeguards are in place at the POC. Subjects will not be contacted outside of what is necessary for the research study.

Potential Benefits

To Subject: The group randomized to steroid administration may experience less or no dysphasia two weeks after the surgery.

To Society: The benefit to society will be publishing the results of the study regardless of whether we see improvement in dysphasia after administration of steroids or no improvement. Other surgeons performing this type of surgery will benefit knowing our results.

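### Is it a defect that the protocol's two analysis models name no covariates, although operated levels and pre-operative swallowing are collected?

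*Protocol*

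**What the plan says.** Data Analysis gives two approaches. The first is introduced with "First, we will look at the time-to-event where the event is" freedom from dysphagia, in a discrete-time survival model. In the second, "we will use a repeated measures ordinal categorical model to assess the effect of steroid/control in a generalized linear model". No other explanatory term is mentioned for either, and none is excluded.

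Other sections bear on the point:

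- The Literature Review names among contributors to postoperative dysphagia "the presence of an anterior plate, the number of operative levels, higher levels of the cervical spine".
- Research Design admits a wide case mix: "This would include persons undergoing anterior cervical discectomy and fusion (ACDF), hybrid constructs, corpectomy(ies), and disc arthroplasty".
- Research Design also says "Other data to be collected for analysis includes patient comorbidities, levels and type of surgery", and on the outcome itself "Swallowing data will be obtained pre-operatively, one day and two days post-operatively".
- Procedures says "Randomization will be performed by the satellite pharmacist outside of the operating room" and mentions no stratification.
- The sample size assumes that "50% of the subjects in the control arm would experience mild, moderate or severe dysphasia" against 20% with steroid at two weeks, with 32 per arm and 81% power.

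**The concern.** The protocol names a prognostic factor, enrols across its whole range, measures it, and then gives it no stated role in either model. With 32 evaluable patients per arm and no stratification described, the arms can differ in number of levels by chance, and an unadjusted estimate carries that difference with it.

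Pre-operative swallowing raises a similar question. The time-to-event outcome is freedom from dysphagia in absolute terms, so a patient who already has symptoms before surgery may reach it later whatever the drug does. The protocol also does not say whether the pre-operative score enters the repeated-measures model as a response or as a covariate.

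At stake would be some precision and protection against an unlucky split, both obtainable from data already being collected.

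**Working it through.** **1. The protocol's own power figure.** Inputs from Data Analysis: 0.50 versus 0.20, n = 32 per arm. Alpha and sidedness are not stated. With the pooled normal approximation,

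power = Φ{[0.30·√32 − z·√(2·0.35·0.65)] / √(0.25 + 0.16)} = Φ{[1.697 − z·0.6745] / 0.6403}.

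- Two-sided 5% (z = 1.960): Φ(0.586) = 72.1%.
- One-sided 5% (z = 1.645): Φ(0.918) = 82.1%. The sample size for 81% power is then 32 per arm.

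The 81% is therefore matched only at one-sided 5%. That is a separate matter and does not depend on covariates. The simulations in steps 3 and 4 use two-sided 5%.

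**2. How likely and how harmful is a chance imbalance?** Assume a factor present in half the patients.

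- SD of the difference in prevalence: √(2·0.25/32) = 0.125. P(15 points or more) = 2[1 − Φ(0.15/0.125)] = 2[1 − Φ(1.2)] = 23%.
- Exact: the difference in counts plus 32 is Binomial(64, 0.5), so P(5 or more patients) = 26%.
- Shift in the 2-week difference = 0.15 × mean within-arm risk difference for the factor, with arm means held at 50% and 20%:
  - OR 2: 0.15 × (0.172 + 0.109)/2 = 2.1 points
  - OR 3: 0.15 × (0.268 + 0.167)/2 = 3.3 points
  - OR 5: 0.15 × (0.382 + 0.231)/2 = 4.6 points

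Against the 30 points sought, that is 7% to 15% of the target effect. The standard error of the unadjusted comparison already allows for such imbalances on average, so the test stays valid.

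**3. What adjustment would gain.** The documents give no covariate–outcome association, so the odds ratio of the factor at two weeks is varied. Simulated power in %, without → with one binary factor of 50% prevalence, at 50% versus 20%:

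| Factor OR | 2-week logistic | Discrete-time survival | Repeated ordinal |
|---|---|---|---|
| 1 | 72 → 72 | 90 → 89 | 99 → 99 |
| 2 | 72 → 73 | 89 → 91 | 99 → 99 |
| 3 | 73 → 75 | 89 → 93 | 98 → 99 |
| 5 | 73 → 78 | 89 → 95 | 98 → 100 |

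At a smaller effect than the trial targets (50% versus 30%), the survival model goes 55 → 56, 55 → 57, 54 → 60 and 55 → 66, and the ordinal model 77 → 76, 75 → 78, 72 → 79 and 71 → 84.

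Caveats on these runs:

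- The control course was 90, 85, 65, 50, 40, 29, 18 and 12.5% over the eight postoperative visits. The figures at two weeks and at 3, 6 and 12 months come from the protocol; the rest are assumed.
- The 40% at four weeks differs from the 50% at one month in the Literature Review. With about 50% there, survival power at OR 1 fell by 2 to 3 points (89 to 87 unadjusted, 89 to 86 adjusted), which leaves the comparison unchanged.
- Type I error was 4.8% to 6.4%. The tests are slightly liberal in places, and adjustment does not cause this.

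**4. Cross-check with two covariates.** A separate simulation of the 2-week outcome used levels and pre-operative dysphagia together. Two-sided power:

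- no information in either: 74.0 → 72.6%, with 3% more variance in the risk difference;
- OR 1.5 per level, 3 for pre-operative dysphagia: 72.3 → 73.4%;
- OR 2 and 3: 73.0 → 75.4% at 10% prevalence of pre-operative dysphagia, 72.4 → 76.3% at 30%;
- OR 3 and 5: 73.1 → 81.3%.

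The approximation n/(1 − R²) agrees: R² = 10% acts like 32/0.90 = 35.6 per arm, and power rises from 72.1% to 76.7%.

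**5. What the text fixes.** The second model is said to assess the effect of steroid versus control. That states the target of inference. Both model classes accept covariates, and Research Design says that levels, type of surgery and comorbidities are collected for analysis. No sentence commits the trial to an unadjusted analysis.

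**The case for a change.** The best case for the concern is that it alleges no error. It asks for two terms, already measured, to be fixed in advance. Naming them early would prevent a choice of covariates after the results are seen, would correct for an imbalance that is not rare at this size, and would settle how the pre-operative score is used. The arithmetic behind it reproduces.

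Much of that stands as good practice. Adjusting for a strong baseline predictor is reasonable, and the person writing the analysis plan may well do it. It does not make the protocol deficient, for three reasons:

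- The covariate list and the handling of the baseline score are details that a protocol commonly leaves to the analysis plan. That plan may already contain them.
- Support for the two terms is uneven. The Literature Review names levels as a contributor without giving a strength. It does not list pre-operative dysphagia, and the protocol gives neither its prevalence nor its prognostic value.
- Adjustment is not entirely free. An uninformative covariate costs a little power, and the adjusted odds ratio becomes conditional on the covariates. Levels as finally performed may also be settled after the first dose, although blinding makes bias from this unlikely.

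The absolute definition of the event does not change this. Randomisation balances pre-operative symptoms in expectation, so they add noise to the comparison between arms, not bias.

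**Conclusion.** The concern does not hold. The protocol states nothing wrong here, contradicts nothing and fixes no poor choice; it is silent on a detail that properly belongs in the statistical analysis plan. The unadjusted comparison is valid under randomisation, and the text leaves adjustment open.

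At the protocol's own effect, one binary factor with an odds ratio up to 5 would change power by about -1 to +6 points. Two covariates would change it by about -1 to +8 points, the upper end needing two strong predictors. Gains above 10 points (55 → 66, 71 → 84) arise only with an odds ratio of 5 and an effect smaller than the one targeted. All these figures rest on two-sided 5%, 32 per arm and assumed covariate strengths. The conclusion does not depend on them: even the largest gain would make adjustment a sensible preference for the analysis plan, not the correction of an error in this protocol.
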